#### Part 2: Monitor more closely the course of respiratory function over time in patients with ALS by using remote pulmonary function testing, performed via telemedicine.

*Primary Hypothesis:* Home respiratory assessment enables thresholds for Non-invasive ventilation (NIV) recommendation to be met in the experimental group significantly closer to the initiation criteria, at a time when quality of life is higher, compared to the control group.

*Secondary Hypothesis:* Telemonitoring of respiratory health in the experimental group will maintain higher quality of life, and lengthen survival.

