## **7.0 Study Design and Procedures**

### **7.1 Study Design**

Part 1: This is a self-controlled study where each participant will be administered a standard of care PFT for measurement of FVC and MIP, as well as an rPFT, separated by at least an hour, for measurement of experimental FVC and MIP. The rPFT is guided by a respiratory therapist in another room, utilizing the telemedicine interface of the Hersey ALS clinic and devices for measuring FVC and MIP (**Error! Reference source not found.**).

Part 2: This is a randomized controlled study to determine whether regular monitoring of respiratory function at monthly, rather than every 3-month intervals, over the course of a year, can lead to better

**Figure 2: (A) Image of the telemedicine interface used by the Hershey ALS clinic. (B) The rPFT toolkit. From left to right: The GiO 4 respiratory pressure meter and mouthpiece, smartphone running the spirometry application, and Air Smart Spirometer and turbine.**

patient outcomes. In the experimental group, standard FVC and MIP measurements obtained by the respiratory therapist in the ALS clinic every 3 months are supplemented with telemedicine-guided rPFT performed at monthly intervals (**Error! Reference source not found. 1**). Controls receive standard PFT assessments only. Patient outcomes, NIV recommendation, quality of life, and survival over one year, will be compared between experimental and control groups.

The researcher and respiratory therapist will be present either in person or virtually for all study sessions and will guide the patient and caregiver in the appropriate use of the equipment. Two devices are used to measure two aspects of respiratory function:

1) Air Smart Spirometer, Pond Healthcare Innovation AB

The following information is paraphrased from the user manual, which is included in the “devices” page of the protocol.

“Air Smart Spirometer is intended to measure the forced expiratory volume in 1 sec (FEV1) and the forced vital capacity (FVC) in a forced expiratory maneuver. These measures can be used for the detection, assessment and monitoring of certain lung diseases. The Air Smart Spirometer is intended to be used by:

- Healthcare professionals trained to perform spirometry tests on patients.
- Adults trained by healthcare professionals or through self-learning who understand how to perform a high quality spirometry test.

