Following the initial visit (month 0), participants will undergo randomization. Those randomized to the experimental group will be shipped an rPFT kit and scheduled for monthly telemedicine appointments between clinic visits. On the dates of the telemedicine appointments, the respiratory therapist administers the study survey and conducts an rPFT from clinic with the patient in their home. This is repeated for the 2nd month. On the 3rd month, the participant dyad is seen by the therapist during their normal clinic visit. This pattern is repeated until the 5th clinical appointment (including the visit at month 0), resulting in 5 in-person assessments and 8 intermediate tele-assessments over the course of approximately 12 months. The control arm will receive standard assessments during regular ALS clinic appointments (Table 1), and be required to complete a study survey each month. Study procedures will be followed until the study endpoint at month 12, even if NIV is initiated during this period. The treating neurologist will make the decision to end the protocol early if the patient is unable to perform the procedures. The patient can also opt to end the study at any time.

The study survey is administered once a month for participants in both study arms and consists of four parts. The initial survey administered at month 0 will be completed with a researcher present. The remaining surveys will be completed online. If it coincides with administration of a PFT or rPFT, it will be administered first. It is designed to measure the impact of daytime breathlessness and sleepiness on QoL and consists of the following components.

- 1) Sleep Apnea Quality of Life Index (SAQLI) - part D [Flemons1998]. It is designed to assess quality of life pertaining to sleep disturbances, as well as the impact of treatment on QoL. It has been used as a sensitive measure of health-related QoL in ALS [Bourke2006, Jackson2001, Bourke2003].
- 2) Motor Neurone Disease Dsypnoea Rating Scale (MDRS) - subscale D [Dorman2007]. Dorman et al. described an ALS-specific assessment, the Motor Neurone Disease Dsypnoea Rating Scale (MDRS), as one with high construct validity and responsiveness. The dyspnea subscale (MDRS-D) of this tool has patients choose which activities of daily living they have experienced shortness of breath in the past two weeks and how severe the episode was [Dougan2000].

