### **8.2 Sample size determination**

Our sample size is predetermined based on our subjective ability to recruit patients within the time frame of the study. Power analysis was based on studies of FVC decline. Lo Coco et al., [LoCoco2006], showed that 50% of study participants dropped below 50% predicted FVC in one year. Given that our exclusion criteria for Part 2 will reject many of the 37% of individuals in their study who were "slow progressors," we estimate that 75% of patients enrolled in our study will meet the respiratory criteria to recommend NIV. This results in a sample size per arm of n=15, which provides 80% power to detect a difference in mean outcome between the two groups if the effect size is found to be 0.95.

Assuming a monthly change in FVC of  $3.5 \pm 3.4\%$  found by Schiffman et al. [Schiffman1993], we conducted 10,000 Monte-Carlo simulations of 40 participants declining at this rate for 12 months. Half were sampled once every three months, and half were sampled every month.  $80.6 \pm 6.3\%$  of simulated participants met the requirements for NIV recommendation, in roughly equal proportions across groups. The average FVC at recommendation was 47.0% predicted in the experimental group, and 43.4% predicted in the control group. The effect size of the difference in FVC between groups was  $.964 \pm .343$ . Similarly, the two measures of QoL obtained at NIV recommendation are powered with an 80% chance to detect improvement of quality of life in the experimental group if the effect size is also found to be 0.95. This corresponds to a mean score difference of 1.52 on the SAQLI, assuming a standard deviation of 1.6 [Flemons1998]. Although there is no published data on the standard deviation of MDRS-D scores, the range and format of questions is similar enough to estimate a comparable difference between groups is needed.

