### **8.3 Statistical methods**

Part 1: The primary hypothesis is that there is no difference in the results of PFT and rPFT for respiratory assessment of FVC and MIP. We will use a paired sample t-test to determine if the mean test results are comparable between the standard and experimental treatments. We will conduct a qualitative analysis to determine whether the patient, caregiver, and therapist determine the rPFT to be an effective way to conduct tests of breathing function.

Part 2: The primary outcomes will be analyzed to determine if respiratory parameters are closer to the actionable threshold at NIV recommendation and whether QoL is better sustained at this point in individuals in the experimental group. This will be done using a non-parametric two sample test of means, the Wilcoxon-Mann-Whitney rank sum test.

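### The only quality-of-life analysis in 8.3 is taken at NIV recommendation; it suits the Part 2 primary hypothesis but leaves the secondary hypothesis of maintained quality of life without an analysis

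*Combined protocol and SAP*

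**What the plan says.** Section 1.1 gives Part 2 two QoL claims. The primary hypothesis is that recommendation comes "at a time when quality of life is higher, compared to the control group". The secondary hypothesis is broader: "Telemonitoring of respiratory health in the experimental group will maintain higher quality of life, and lengthen survival".

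Section 7.1 adds: "Patient outcomes, NIV recommendation, quality of life, and survival over one year, will be compared between experimental and control groups".

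Under 7.2.2 both arms complete the survey monthly from month 0, and "Study procedures will be followed until the study endpoint at month 12, even if NIV is initiated during this period".

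The Part 2 paragraph of 8.3 is confined to the primary outcomes. Its QoL element asks "whether QoL is better sustained at this point in individuals in the experimental group", using a two-sample rank-sum test. Section 8.2 likewise powers QoL only at recommendation. No section gives a method for the repeated surveys, for QoL at month 12, or for patients who are never recommended NIV.

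**The concern.** A score at recommendation and QoL maintained over follow-up are different quantities. The 8.3 test cannot supply the second, for three reasons.

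- **Who is included.** Only patients who reach recommendation contribute, and that event occurs after randomisation. Section 8.2 states: "we estimate that 75% of patients enrolled in our study will meet the respiratory criteria to recommend NIV".
- **When they are measured.** Monthly testing is meant to catch the threshold sooner, so the arms are compared at different disease stages: "The average FVC at recommendation was 47.0% predicted in the experimental group, and 43.4% predicted in the control group".
- **What is left out.** No survey after recommendation enters the test, yet that is when a benefit of earlier NIV would show.

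A higher experimental score at recommendation is a fair sign that recommendation came earlier. It can arise when QoL followed the same course in both arms, so it does not show that QoL was maintained. A trial that follows 8.3 exactly would have no prespecified basis for a statement on its secondary QoL hypothesis. With 13 survey months and several scales, a method chosen afterwards would be open to selection.

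**Working it through.** **1. Reproducing the plan's figures.** From 8.2: 0.75 × 20 = 15 evaluable patients per arm, and 0.95 × 1.6 = 1.52 SAQLI points. Alpha and sidedness are not stated. At n = 15 and effect size 0.95, a t-test has 81.4% power one-sided at 5% and 70.9% two-sided, so the plan's 80% corresponds to a one-sided test. The point here does not depend on that.

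The FVC simulation was rebuilt with a monthly loss of 3.5 (SD 3.4) redrawn each month, tests monthly or every three months, and recommendation at the first FVC of 50% or less. Baseline FVC is not given in 8.2, so four distributions were assumed.

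| | Plan (8.2) | Rebuilt, four baselines |
|---|---|---|
| Recommended | 80.6% | 80.2-81.6% |
| FVC at recommendation, experimental | 47.0 | 47.0 |
| FVC at recommendation, control | 43.4 | 43.1-43.5 |
| Effect size | 0.964 | 0.94-1.00 |

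Both arms decline identically in the rebuilt model. The FVC gap therefore comes from the testing interval alone.

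**2. Data used.** Planned surveys: 13 × 40 = 520. The 8.3 test uses one per recommended patient: 0.75 × 40 = 30, or 0.806 × 40 = 32. It leaves out 8-10 of 40 patients and, in the rebuilt model, 85-169 surveys completed after recommendation.

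**3. What the test shows when QoL courses are identical.** Assume SAQLI falls by *b* points per FVC point, equally in both arms, with SD 1.6 at recommendation. The documents give no value for *b*, so a range is shown. With the plan's FVC gap of 47.0 − 43.4 = 3.6:

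- difference at recommendation = 3.6*b*
- noncentrality = (3.6*b* / 1.6) × √(15/2)
- P(favours experimental) ≈ P(Z > 1.96 − noncentrality), two-sided 5% test

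| *b* | Difference | Noncentrality | By formula | Simulated rank-sum | Yearly SAQLI loss (*b* × 3.5 × 12) |
|---|---|---|---|---|---|
| 0.02 | 0.07 | 0.12 | 3.3% | 3.2-3.4% | 0.8 |
| 0.05 | 0.18 | 0.31 | 4.9% | 4.5-5.1% | 2.1 |
| 0.1 | 0.36 | 0.62 | 9.0% | 7.8-8.5% | 4.2 |
| 0.2 | 0.72 | 1.23 | 23% | 20-24% | 8.4 |

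The nominal rate is 2.5%. The simulation used 8,000 trials of 20 against 20 per cell, with residual variance split 70/30 between patient and noise (assumed). The last row implies a yearly loss of 8.4 / 1.6 = 5.25 SDs, so it is an upper extreme.

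**4. Which comparison of all randomised patients.** Under the same identical courses:

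- *Unequal dropout (25% against 5%, assumed).* A rank comparison of each patient's mean over months 1-12 favours the experimental arm in 2.2-8.0% of trials. A month-by-arm mean difference with patient-level standard errors stays at 2.2-2.8%.
- *Survey mode.* At tele-visits "the respiratory therapist administers the study survey and conducts an rPFT from clinic with the patient in their home", in the experimental arm only, although 7.2.2 also says surveys after month 0 are completed online. An assumed 0.5-point shift at those eight visits takes the months 1-12 rank comparison to between 6% and 20%, depending on the deaths and dropout assumed. Using months 3, 6, 9 and 12 only, it stays at 2.2-2.8%.

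These results favour repeated measures over ranks, and clinic months over all months. The two features were checked separately, not in combination.

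**5. Precision.** For one time point with 20 per arm and SD 1.6, the 95% half-width is 2.024 × 1.6 × √(2/20) = 1.02 SAQLI points. The simulated month-by-arm mean difference had half-widths of 0.61-1.11 points.

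**The case against.** Section 8.3 does not claim what the concern guards against. Its sentence is tied to the point of recommendation and its paragraph to the primary outcomes. A reader might infer that the rank-sum test is invalid, or that 8.3 offers it as proof of maintained QoL. The documents support neither: the test answers the primary hypothesis as 1.1 words it.

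A reader might also infer that 7.1 firmly promises a one-year QoL comparison. The words *over one year* there may belong to survival alone. Section 7.1 still says QoL will be compared between arms, and on either reading the secondary hypothesis in 1.1 has no method.

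The numerical effect is modest. At slopes of 0.02-0.05 the shift is 0.07-0.18 points, about 5-12% of the plan's 1.52. The model follows the FVC route only. Section 7.2.2 also recommends NIV for dyspnea with MIP above −60 cm H₂O, which can only add recommendations or bring them forward, so the counts of omitted patients and surveys are approximate.

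Finally, a trial sized by what could be recruited is unlikely to settle the secondary question. That stands, but it bears on how much to expect from the analysis, not on whether to specify it.

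**Conclusion.** The point holds as a gap between hypothesis and analysis, and it should be fixed. The gap itself is read directly from 1.1, 7.2.2 and 8.3 and needs no simulation.

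The false-signal rates apply only if the at-recommendation result is read as evidence of maintained QoL. They are about 3-5% at modest slopes, 8-9% at 0.1, and about 20% only at an extreme slope, against 2.5%. They are not error rates for the primary hypothesis, and it would be wrong to quote the 20% figure as the expected size. They rest on assumed slopes, baselines and variance split, and on a two-sided 5% test. The exclusion of 20-25% of patients and the FVC gap of 3.6 points come from the plan's own figures in 8.2.

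**What to change.** Add one secondary analysis to 8.3:

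- **Comparison.** Repeated-measures comparison of SAQLI part D in all randomised patients, adjusted for the month 0 score, reporting the between-arm mean difference with a 95% CI. Analyse MDRS-D and SF-36 the same way, naming the SF-36 score to be used.
- **Data.** All completed surveys at the analysed months, including those from withdrawn patients (even if replaced under 3.3.2) and those after NIV starts.
- **Months.** Months 3, 6, 9 and 12 as the main analysis, because survey mode may differ between arms at the tele-visit months; all months 1-12 as a sensitivity analysis.
- **Deaths.** Report by arm alongside. A ranking with deaths placed worst is an optional sensitivity analysis where death dates are known, since 3.3.2 gives withdrawn patients no follow-up.
- **Wording.** Base any statement that telemonitoring maintains QoL on this analysis, and describe the existing test as QoL at the time of recommendation.

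The primary analysis is unchanged. The cost is a paragraph and a modest extra analysis of data already collected, with no new visits. The downside is an imprecise and probably inconclusive estimate at 20 per arm.

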## **9.0 Confidentiality, Privacy and Data Management**

Please see HRP-598 Research Data Plan Review Form

## **10.0 Data and Safety Monitoring Plan**

N/A

## **11.0 Risks**

The risks posed to subjects in the study will be no different than those presented during standard of care administration of pulmonary function testing. At all times participants will complete the study procedures under the guidance of a licensed respiratory therapist. In addition to expert guidance, those participating in remote assessments will be required to have a caregiver present to aid the patient in case assistance is required.

Loss of confidentiality is a risk of this study, but steps are taken to protect the participants' identities. Personal information, clinical assessments, test results, and survey responses will be labeled with a participant code assigned by REDCap and stored in this database. All data containing PHI will be collected either from the electronic medical record or in person. Data transmitted through the Air Smart Spirometer app will be labeled with the user's subject code, gender, age, and height. No part of the telemedicine video or audio recordings will be permanently stored.

## **12.0 Potential Benefits to Subjects and Others**

### **12.1 Potential Benefits to Subjects**

The experimental group in Part 2 may benefit from improved quality of life and survival.

### **12.2 Potential Benefits to Others**

This knowledge gained by this study may benefit those who are managed remotely using telemedicine. This will enable virtual care to be more equivalent to in-person care.

## **13.0 Sharing Results with Subjects**

Participants will be informed of the results of their breathing tests at each visit. The respiratory therapist and nurse clinician will be responsible for making appropriate recommendations around those results, and following up with the neurologist for NIV recommendation if necessary.

Participants will not be informed of overall study results unless they request it. Study results include the public presentation of research at academic conferences or through peer-reviewed journals.

## **14.0 Subject Stipend (Compensation) and/or Travel Reimbursements**

There will be no compensation in Part 1. For Part 2, the participant team will be compensated \$5 per completed survey and \$10 per rPFT administration. They will be paid for the sessions they complete, with total compensation capped at \$65 for those in the control arm and \$145 for those in the experimental arm. Subjects will be required to provide their social security number and address for payment

## **15.0 Economic Burden to Subjects**

### **15.1 Costs**

As a part of the normal study procedures, subjects will incur no cost for their participation. The participant team will be loaned research equipment owned by Penn State University. If damage were to come of this equipment, Penn State University or their insurer might seek recovery for these costs from the patient's homeowner's insurance policy if it was found that they were at fault for the damage.

### **15.2 Compensation for research-related injury**

It is the policy of the institution to provide neither financial compensation nor free medical treatment for research-related injury. In the event of injury resulting from this research, medical treatment is available but will be provided at the usual charge. Costs for the treatment of research-related injuries will be charged to subjects or their insurance carriers.

## **16.0 Resources Available**

### **16.1 Facilities and locations**

For Part 1, the consent procedure will be conducted within the ALS Clinic at [name] on the Hershey Medical Center campus. The clinic houses a room set up by the Penn State Hershey information technology department that is dedicated to ALS telemedicine. This room will also be used as the site for the respiratory therapist to conduct the rPFT assessment. This research room is in a private location and contains all the tools necessary for engaging in secure videoconferencing.

For Part 2, consent may be obtained in the ALS clinic or over the telemedicine interface. The home of the patient will be the site of most of the study procedures for the participant team. A member of the study team and the respiratory therapist will communicate with the participant team over the telemedicine interface in the research room of the ALS clinic.

### **16.2 Feasibility of recruiting the required number of subjects**

We anticipate high interest in Part 1 due to the short time commitment and participation during a single clinical visit. We anticipate no issues recruiting 40 individuals for this study. The resource and timing limitations of Part 2 will make enrollment more challenging. Forty participants, half of which will be randomized to the experimental group, will take place in this year-long study. We anticipate the participation of two respiratory therapists to aid with rPFT administration.

### **16.3 PI Time devoted to conducting the research**

The PI has devoted 5% time to oversight of this project, involving discussion the goals, procedures, analysis, and data review, as well as input on clinical matters as requested by members of the study team.

#### **16.4 Availability of medical or psychological resources**

If any medical or psychological resources are found to be needed during the course of the study, the participant will be directed to contact his/her Primary Care Provider or emergency care if warranted.

#### **16.5 Process for informing Study Team**

Before recruitment and any time a change is made to the protocol, the study team will meet to discuss changes in their role within the study, if applicable.

### **17.0 Other Approvals**

#### **17.1 Other Approvals from External Entities**

N/A

#### **17.2 Internal PSU Committee Approvals**

**Check all that apply:**

- Anatomic Pathology – Hershey only – Research involves the collection of tissues or use of pathologic specimens. Upload a copy of HRP-902 - Human Tissue For Research Form on the “Supporting Documents” page in CATS IRB. This form is available in the CATS IRB Library.
- Animal Care and Use – All campuses – Human research involves animals and humans or the use of human tissues in animals
- Biosafety – All campuses – Research involves biohazardous materials (human biological specimens in a PSU research lab, biological toxins, carcinogens, infectious agents, recombinant viruses or DNA or gene therapy).
- Clinical Laboratories – Hershey only – Collection, processing and/or storage of extra tubes of body fluid specimens for research purposes by the Clinical Laboratories; and/or use of body fluids that had been collected for clinical purposes, but are no longer needed for clinical use. Upload a copy of HRP-901 - Human Body Fluids for Research Form on the “Supporting Documents” page in CATS IRB. This form is available in the CATS IRB Library.
- Clinical Research Center (CRC) Advisory Committee – All campuses – Research involves the use of CRC services in any way.
- Conflict of Interest Review – All campuses – Research has one or more of study team members indicated as having a financial interest.
- Radiation Safety – Hershey only – Research involves research-related radiation procedures. All research involving radiation procedures (standard of care and/or research-related) must upload a copy of HRP-903 - Radiation Review Form on the “Supporting Documents” page in CATS IRB. This form is available in the CATS IRB Library.
- IND/IDE Audit – All campuses – Research in which the PSU researcher holds the IND or IDE or intends to hold the IND or IDE.
- Scientific Review – Hershey only – All investigator-written research studies requiring review by the convened IRB must provide documentation of scientific review with the IRB submission. The scientific review requirement may be fulfilled by one of the following: (1) external peer-review process; (2) department/institute scientific review committee; or (3) scientific review by the Clinical

Research Center Advisory committee. NOTE: Review by the Penn State Hershey Cancer Institute Scientific Review Committee is required if the study involves cancer prevention studies or cancer patients, records and/or tissues. For more information about this requirement see the IRB website at: <http://www.pennstatehershey.org/web/irb/home/resources/investigator>

